In approximately 30% of SM patients, an AHNMD (myeloid malignancy) is diagnosed. The subvariant categories of AHNMD include SM-AML (acute myeloid leukemia), SM-MDS (myelodysplastic syndrome), SM-MDS/MPN (MDS/myeloproliferative neoplasm, eg, chronic myelomonocytic leukemia), and SM-HES or SM-CEL (hypereosinophilic syndrome or chronic eosinophilic leukemia). Generally, separate treatment plans for the SM and the AHNMD should be established for these patients. However, the SM and AHNMD may share a common pathophysiologic link, and particular treatments may be useful for both the SM and myeloid malignancy. Although the intent of SM-directed therapy is to target neoplastic mast cells, it may not always be possible to identify whether organ damage is due to the SM or AHNMD component or both. Patients with CEL-associated with the FIPL1-PDGFR α fusion gene may exhibit increased mast cells in the bone marrow but are not classified by the WHO as having systemic mastocytosis. It is recommended that such patients be treated with imatinib ([Valent et al. 2007](#)) and would not be considered eligible for this protocol.

The most important growth factor for mast cells seems to be stem cell factor (SCF) also termed mast cell growth factor or KIT ligand. SCF induces the development of mast cells from their uncommitted CD34+ progenitors. The effects of SCF on mast cells and mast cell

progenitors are mediated through KIT, a tyrosine kinase receptor (for SCF) encoded by the KIT proto-oncogene. SCF and SCF-dependent activation of KIT are essential to the development and differentiation of mast cells. “Gain-of-function mutations” in the kinase domain of *KIT* are associated with enhanced growth of mast cells and their progenitors. Such mutations (eg, D816V) are frequently detected in patients with SM ([Valent et al. 2005](#)).

Specific gene defects are well recognized as the oncogenic factors in SM. The *KIT* D816V mutation expressed in neoplastic mast cells is by far the most common and is found in all variants of SM. Highly sensitive methods have detected that >90% of patients with SM carry the D816V *KIT* mutation. Several other *KIT* gene defects have been identified in patients with mast cell disease, but each are likely to be present in less than 5% of diagnosed patients ([Sotlar et al. 2003](#), [Garcia-Montero et al. 2006](#), [Valent et al. 2005](#)).

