2.3.2 Secondary Efficacy Endpoints

- Immunohistochemical expression of CD30 on neoplastic mast cells in core biopsy samples or by flow before SGN-35 treatment and after 4 and 8 cycles of therapy
- Total symptom score and QOL score using a modified Myeloproliferative Neoplasm Symptom Assessment Form (MPN-SAF)
- Duration of response (DoR) is defined as the time from first onset of confirmed response to the date of first documented and confirmed progression or death due to ASM/MCL. Time to response (TTR) is defined as the time from start of treatment until the date of onset of a confirmed response
- Progression-free survival (PFS) is defined as the time from start of treatment to the date of the first documented and confirmed progression or death or institution of new therapy

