7.6.4 Duration of Response (DoR) and Time to Response (TTR)

The duration of (confirmed) overall response (DoR) is defined as the time from the start of the first confirmed response until the date of the first documented and confirmed disease progression or death due to ASM or MCL. The Kaplan-Meier product-limit method will be used to summarize the response duration. If a patient did not progress or die due to ASM or MCL at the time of the analyses, DoR will be censored at the date of the last adequate response assessment.

Time to response (TTR) is defined as the time from the date of start of treatment to the date of first confirmed response. Time to response will be censored at the date of the last adequate response assessment in patients did not progress or die due to any cause and at maximum follow-up date (ie, date of first patient first visit (FPFV) to date of last patient last visit (LPLV) used for the analysis) in patients who progressed or died due to any cause. Kaplan-Meier product-limit estimates will be used to summarize the time to response.

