7.6.5 Progression-free survival (PFS) and overall survival

Progression-free survival (PFS) is defined as the time from the date of start of treatment until the date of first documented confirmed disease progression or death or institution of new therapy. If a patient did not progress or die due to any cause at the time of the analyses, PFS will be censored at the date of the last adequate response assessment. Kaplan-Meier product-limit estimates will be used to summarize PFS. For overall survival, patients will be contacted every 6 months until the study closure or death.

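### New therapy ends PFS but neither ends nor censors duration of response, so time under another treatment can be reported as response duration

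*Combined protocol and SAP*

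**What the plan says.** Section 2.3.2 runs DoR from the onset of a confirmed response to "first documented and confirmed progression or death due to ASM/MCL". Section 7.6.4 repeats those two end points ("until the date of the first documented and confirmed disease progression or death due to ASM or MCL"). For patients with neither, it says that "DoR will be censored at the date of the last adequate response assessment". It does not define an adequate assessment or limit it to the time before other treatment.

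PFS has a wider list of end points. Section 2.3.2 ends it at "progression or death or institution of new therapy", and section 7.6.5 runs it "until the date of first documented confirmed disease progression or death or institution of new therapy". The next sentence of 7.6.5, on censoring, names only progression and death and omits new therapy.

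Three other places bear on the point. Section 4.4 bars other anti-cancer agents while a patient is on study, but permits hydroxyurea for a raised leukocyte count from a concurrent myeloid neoplasm. Sections 4.3 and 4.6.1 keep patients under six-monthly survival contact until death or study closure. On patients with an associated hematological disease (AHNMD), section 1.1 remarks: "Generally, separate treatment plans for the SM and the AHNMD should be established for these patients".

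**The concern.** The two endpoints disagree on what happens when a responder moves to another treatment. By its definition PFS stops that day. DoR has no rule for it, so the response clock continues. If the patient later dies of ASM or MCL without an earlier confirmed progression, the DoR event is dated to the death. The interval under the other treatment is then reported as durability of the SGN-35 response.

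DoR is one of the few measures of lasting benefit in a study of 11, at most 26, patients. The Kaplan-Meier curve will rest on a handful of responders, so a single long interval of this kind can change what is reported. The point concerns non-protocol therapy started during a response. It does not concern loss of response or re-treatment with SGN-35.

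**Working it through.** The plan gives no median, rate or sample size for DoR or PFS, so it has no figure to reproduce. The check compares the definitions and then uses assumed dates.

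**1. Definitions side by side**

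| | DoR (2.3.2, 7.6.4) | PFS (2.3.2, 7.6.5) |
|---|---|---|
| Confirmed progression | event | event |
| Death from ASM/MCL | event | event |
| Death from another cause | not an event | event |
| New therapy | not mentioned | event by definition; missing from the censoring sentence |

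**2. One patient.** In weeks from first dose, let *a* be response onset, *n* new therapy and *d* death from ASM/MCL, with no progression recorded.

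- PFS = *n*
- DoR as written = *d* − *a*
- DoR ended at new therapy = *n* − *a*
- Time under other treatment counted as response = *d* − *n*

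With assumed values *a* = 9, *n* = 40, *d* = 104: PFS = 40; DoR as written = 104 − 9 = 95; DoR ended at new therapy = 40 − 9 = 31; difference = 104 − 40 = 64 weeks.

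The response end date (*d*) always falls after the PFS end date (*n*). DoR is the longer interval only if *d* − *n* exceeds *a*. I took onset at 3, 9 or 24 weeks, new therapy at 30, 40 or 52, and death at 52, 78 or 104. I kept combinations with death after new therapy and at least 12 weeks of response before it, because section 4.7.1 requires 12 weeks for confirmation. That leaves 21 combinations. DoR as written is 28 to 101 weeks, against 16 to 49 if ended at new therapy, with PFS 30 to 52. DoR exceeds PFS in 20 of the 21; the exception is 24/40/52, with DoR 28 and PFS 40.

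**3. Five responders.** Four have assumed DoR events at 16, 24, 40 and 60 weeks. The fifth is the patient in step 2.

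| Handling of the fifth patient | Median | Still in response after week 40 | After week 60 |
|---|---|---|---|
| As written (event at 95) | 40 | 2/5 = 0.40 | 1/5 = 0.20 |
| Event at new therapy (31) | 31 | 1/5 = 0.20 | 0 |
| Censored at new therapy (31) | 40 | 3/5 × 1/2 = 0.30 | 0 |

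One patient changes the curve under either alternative. The median moves only if new therapy is an event.

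**4. Effect on the median in a large sample.** All inputs are assumptions: exponential times, median 12 months from response to progression, median 18 months from new therapy to ASM/MCL death, 48 months of follow-up, and 19% or 33% of responders starting new therapy before progression.

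- *New therapy as an event.* The two hazards add, so the median is 12 × (1 − share): 12 × 0.81 = 9.7 and 12 × 0.67 = 8.0 months.
- *Censored at new therapy.* Censoring is independent of progression here, so the median stays at about 12.0 months for both shares.
- *As written*, with ASM/MCL deaths within 48 months counted and other patients who switch censored when they switch: 12.1 and 12.2 months by simulation. If they stay at risk to death or month 48, the values are 12.3 and 12.7. If progression can also be recorded after new therapy, they are 11.5 and 11.0.

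The gap to the event rule is 12.1 − 9.7 = 2.4 and 12.2 − 8.0 = 4.2 months. The gap to the censoring rule is 0.1 and 0.2 months.

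**The case against.** The strongest reply has four parts.

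*The two endpoints are different composites.* DoR is disease-specific and PFS is not; they already differ on deaths from other causes. Different end dates are not a logical contradiction, and how to treat new therapy is a choice of estimand. This stands. A reader might infer that a response can never outlast PFS, but the definitions do not imply that. What remains is that the plan makes the choice for PFS and is silent for DoR.

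*The route is narrow.* Section 4.4 bars other anti-cancer agents on study, and only survival contact is scheduled after a patient leaves, so response assessments after new therapy are not planned. AHNMD needing immediate cytoreductive or targeted therapy is excluded at entry (3.3.2), and transformation of a chronic myeloid neoplasm to AML counts as progression (Appendix G). All this reduces exposure. It leaves open a later ASM/MCL death in a patient without recorded progression, which 7.6.4 makes a DoR event. The survival follow-up text does not mention cause of death, but the DoR definition cannot be applied without it.

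*Inflation is not shown.* A reader might infer from step 4 that median DoR is overstated by 2 to 4 months. It is not: the assumed true median is 12 months, the as-written result is close to it, and censoring gives almost the same value. The gap measures the choice of event over censoring. Nor does the AHNMD share of about 30% in section 1.1 supply a rate: it is a prevalence among SM patients, not the proportion starting new therapy while responding.

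*No decision depends on DoR.* The rules in section 7.8 (2 of 11, then 5 of 26) use response counts only. This is correct and limits the consequence to reporting.

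**Conclusion.** The point holds as an inconsistency between two secondary endpoints. New therapy is an end of PFS in both of its definitions; it is neither an end nor a censoring point for DoR in either of its own. Applied literally, the plan can date a responder's DoR event to an ASM/MCL death long after that patient's PFS ended (64 weeks later in the illustration, on assumed dates). That part rests on the text alone.

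The size across the trial is unknown. The documents give no rate of new therapy during response, and the effect on the median runs from negligible to several months depending on whether new therapy is an event or a censoring point. No figure for inflation should be quoted. With few responders, one such patient can still alter the curve. The primary endpoint and the two-stage design are unaffected.

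**What to change.** In sections 2.3.2 and 7.6.4, end DoR at institution of new therapy, to match the protocol's own PFS definition. State that no response assessment or death after that date contributes to DoR. Add a sensitivity analysis that censors DoR at the last adequate response assessment before new therapy, and report both, since step 4 shows that the choice can matter more than anything else here.

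In the same edit:

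- Add new therapy to the PFS censoring sentence in 7.6.5. At present a patient who starts new therapy without progression or death is an event by the definition and censored by the sentence after it.
- State for both endpoints whether the hydroxyurea use permitted in section 4.4 counts as new therapy. Otherwise a treatment allowed on study could end both endpoints, or not, according to who reads the rule.

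The cost is wording. The start date of new therapy is already needed for PFS. The drawback is a somewhat shorter reported DoR, because a patient still responding when other treatment begins will count as having reached the end of response.

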7.1 Populations

Two populations will be considered for the evaluation of this study:

1. The primary efficacy population includes all patients who have received at least 1 dose of SGN-35.
2. The safety population includes all patients in the study who received at least one dose of SGN-35. The safety population will be used for all safety analyses.

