7.5 Primary Objective- Efficacy evaluation

The efficacy of the regimen will be assessed in this study. The primary efficacy endpoint is response rate. A responder is an ASM or mast cell leukemia patient (with or without an AHNMD) who experiences a complete or partial remission, or clinical improvement per international consensus response criteria. Patients with stable disease (SD) or progressive disease (SD) are considered non-responders (NR). Patients with missing tumor assessment or who die or discontinue the study before having their first assessment will be considered non-responders. Best clinical response will be tabulated. The rate of complete remission, partial remission, and clinical improvement (CI) will be estimated and its 95% confidence interval will be provided.

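### Time to response (7.6.4) drops early stoppers without progression or death from the risk set, so its Kaplan-Meier curve can end above the trial's own response rate

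*Combined protocol and SAP*

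**What the plan says.** Section 7.6.4 divides patients without a confirmed response into two groups.

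- No progression and no death: "Time to response will be censored at the date of the last adequate response assessment in patients did not progress or die" from any cause.
- Progression or death: censored at the maximum follow-up date "used for the analysis) in patients who progressed or died due to any cause". These patients stay in the risk set throughout. The death clause has no time limit.

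The estimator is stated as: "Kaplan-Meier product-limit estimates will be used to summarize the time to response". No separate rule covers a patient who stops treatment early without progression.

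The primary analysis treats the same patients differently. Section 7.1 sets the denominator: "The primary efficacy population includes all patients who have received at least 1 dose of SGN-35". Section 7.5 then says "Patients with stable disease (SD) or progressive disease (SD) are considered non-responders (NR"), where the second SD evidently stands for PD. It adds: "Patients with missing tumor assessment or who die or discontinue the study before having their first assessment will be considered non-responders". The last sentence covers patients who stop before any assessment; the one before it covers those who stop later with stable disease.

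Section 3.2 counts a response only if it starts by the end of cycle 8 and lasts at least 12 weeks. Section 4.3 lists the reasons for stopping early, including adverse events, withdrawn consent and loss to follow-up. It has these patients followed for survival every 6 months.

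**The concern.** Censoring in a Kaplan-Meier analysis assumes that the censored patient would go on to respond at the same rate as those still at risk. That is reasonable for a patient still being assessed at the data cut. It is not reasonable for one whose response assessments have ended without a response, because no later response can be observed or counted. The plan accepts this for progression and death by holding those patients at risk to maximum follow-up, but does not extend it to early stops for other reasons.

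Two results of the same trial can then disagree. The response rate divides responders by all dosed patients, while the TTR curve can end higher. The curve also depends on the data cut. When an early stopper dies, perhaps long after the response window has closed, the patient moves to the maximum-follow-up group and the curve is redrawn from that patient's earlier censoring date onward, with no new information on response. With 11 to 26 patients, a few early stops are enough to show.

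**Working it through.** **Plan's own figures.** The documents state no figure for TTR. The nearest are those of the two-stage design in 7.8, which also fix the sample sizes used here. With X1 ~ Bin(11, p) and X2 ~ Bin(15, p), early stopping is P(X1 ≤ 1), and acceptance is the sum over x = 2 to 11 of P(X1 = x)·P(X2 ≥ 5 − x).

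- p = 10%: early stopping 69.7% (stated 70%), alpha 8.65% (stated 8.7%).
- p = 30%: early stopping 11.3% (stated 11%), power 85.2% (stated 85%).

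All four reproduce. They use counts of responders only, so TTR does not enter them.

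**Why the direction is fixed.** The TTR estimate is 1 − ∏(1 − d_j/n_j), with d_j responses and n_j patients at risk at each response time. If every non-responder stays at risk past the last response, the product telescopes to (n − r)/n and the curve ends at r/n, the response rate. Removing an early stopper lowers each later n_j, leaves d_j unchanged and so raises the estimate. If no response follows the removal, nothing changes. Patients who complete 8 cycles with stable disease (8 × 3 = 24 weeks without delays) are censored when no new response can count, so they cause no excess.

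**Inputs.** Sample sizes come from 7.8 and the censoring rule from 7.6.4. Response times, stop times and stop shares are assumptions.

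**Example, n = 11.** Responses at weeks 6, 12 and 18; early stops without progression last assessed at weeks 3, 6.5 and 9; 3 patients progressed; 2 completed with stable disease.

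- Response rate: 3/11 = 27.3%.
- At risk at the three response times: 10, 7, 6. Estimate: 1 − (9/10)(6/7)(5/6) = 35.7%.

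The same data as early stoppers later die, earliest stop first:

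| Early stoppers since dead | Calculation | Estimate |
|---|---|---|
| 0 | 1 − (9/10)(6/7)(5/6) | 35.7% |
| 1 | 1 − (10/11)(7/8)(6/7) | 31.8% |
| 2 | 1 − (10/11)(8/9)(7/8) | 29.3% |
| 3 | 1 − (10/11)(9/10)(8/9) | 27.3% |

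**Milder cases, n = 11, 3 responders.**

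- One early stop at week 3: 1 − (9/10)(8/9)(7/8) = 30.0%, returning to 27.3% if that patient dies.
- All three responses before the first early stop: 1 − 8/11 = 27.3%, equal to the response rate.

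**Example, n = 26.** 5 responses at weeks 6, 9, 12, 15 and 18; 6 early stops at weeks 3, 3, 6.5, 6.5, 9.5 and 12.5. The estimate is 1 − (23/24)(20/21)(18/19)(16/17)(15/16) = 23.7%, against 5/26 = 19.2%.

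**Range over the unknown stop share.** Simulation with 6,000 trials per cell and a true response rate of 30%. Response onset was spread evenly over weeks 3 to 24 and early stoppers' last assessments over weeks 0 to 21.

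| Share stopping early without progression | Mean estimate, n = 11 | Mean estimate, n = 26 | Trials with estimate above response rate, n = 11 / n = 26 |
|---|---|---|---|
| 0% | 30% | 30% | 0% / 0% |
| 10% | 32.1% | 32.0% | 58% / 91% |
| 20% | 34.4% | 34.6% | 81% / 99% |
| 30% | 37.4% | 37.8% | 90% / 99.9% |

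**The case against.** The strongest reply is that little depends on this curve. TTR is secondary and descriptive, carries no test, and stands beside a response rate with a 95% confidence interval on all dosed patients. This stands, and it limits the point to a reporting defect. A reader might infer that the go/no-go decision is biased, or that a less tolerable drug would be judged more active. The documents do not support either: the decision rules count responders, and this single-arm trial makes no comparison on TTR.

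Second, stopping treatment is not the same as becoming unable to respond. Section 3.2 does not require ongoing dosing, and Table 2 schedules response assessments at end of treatment and, for non-responders, about 30 days later. This also stands. The relevant event is therefore the end of response assessment without a response. After that only survival follow-up remains, so the mechanism holds.

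Third, Table 1 mostly calls for holding or reducing the dose before discontinuation, so very early toxicity stops may be few. Fewer or later stops shrink the excess, as the one-stop and zero-excess cases show. But 4.3 also lists stops unrelated to toxicity.

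Fourth, later deaths move the curve towards the response rate. That is true, but the result still depends on when the data are cut.

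A reader might also infer that TTR has two competing end dates, onset and confirmation, because 7.6.4 refers to the date of first confirmed response. The plan settles this. Section 2.3.2 says "Time to response (TTR) is defined as the time from start of treatment until the date of onset of a confirmed response", and 4.7.1 dates a response by its actual date.

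**Conclusion.** The concern holds in a conditional form. Once response assessment has ended for all patients, the 7.6.4 curve cannot end below the response rate, and it ends above it if at least one response starts after an early stopper's last assessment. A reader might infer that the two must always differ; they are equal when all responses come first.

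In the 11-patient example with three early stops the excess is 35.7 − 27.3 = 8.4 percentage points; with one it is 2.7 points. At a true rate of 30%, the average excess is about 2, 4 to 5, and 7 to 8 points for early-stop shares of 10%, 20% and 30%. Those shares and the timing are assumptions, since the documents give neither. The dependence on later deaths needs no assumption about size: it follows from the open-ended death clause together with continued survival follow-up.

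The primary response rate and the 2/11 and 5/26 rules are unaffected. The change is worth making before analysis but does not threaten the trial's main conclusion.

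**What to change.** In 7.6.4, replace the TTR censoring sentence and estimator along these lines:

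- Estimate TTR by cumulative incidence of confirmed response, with progression, death and end of response assessment without a response as competing events.
- Alternatively, censor at maximum follow-up every patient who can no longer have a countable response. This gives the same curve once no patient is pending.
- Under either option, keep patients censored at their last adequate assessment if, at the data cut, they are still under response assessment or have an unconfirmed response awaiting 12-week confirmation. Without this exception, responses starting in cycles 6 to 8, which 4.7.1 follows through post-treatment visits, would be treated as permanent failures at an early cut such as the interim analysis.
- Report the median and range of TTR among responders.

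Once all patients are resolved, the curve ends at the response rate (27.3% and 19.2% in the examples) and no longer moves with later deaths. The cost is a few sentences and a redefined censoring variable, with no new data. The TTR curve becomes less favourable.
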